11.1. Safety Parameters

The safety parameters to be utilized in this study are listed below. The schedule for their assessment is listed in [Table 4](#) and [Section 6.1.1](#).

1. Local and systemic vaccine reactogenicity.
2. Laboratory Safety Evaluation
3. Medical History and Physical Examination

11.1.1. Demographic/Medical History

A complete medical history will be conducted on all volunteers prior to enrollment. The medical history will include a review of body systems, determination of any current symptoms or conditions, and documentation of any concurrent medications and other treatments that might preclude the volunteer from participation in the study. It will also include a review of the volunteer's prior medical record. A complete physical examination will consist of an exam including evaluations of the following: general appearance, skin, HEENT, extremities, heart, lungs, lymph nodes, and abdomen; additional examination based on history and symptoms. A directed physical examination will be performed at interim visits as noted in the protocol and [Table 4](#) Schedule of Assessments and will include examinations of the injection site(s) and lymph nodes with special attention to the axillary lymph nodes. In addition, physical manifestations of any previously noted condition or adverse experience will be evaluated.

11.1.2. Vital Signs

Vital signs will be taken at the study visits as outlined in [Section 6.1.1](#).

11.1.3. Weight and Height

Weight and height will be taken at the study visits as outlined in [Section 6.1.1](#).

11.1.4. Physical Examination

A complete physical examination will be conducted on all volunteers prior to enrollment. A complete physical examination will consist of evaluations of the following: general appearance, skin, HEENT, extremities, heart, lungs, lymph nodes, and abdomen; additional examination based on history and symptoms. A directed physical examination will be performed at interim visits as noted in the protocol ([Section 6.1.1](#) and [Table 4](#)) and will include examinations of the injection site(s) and lymph nodes with special attention to the axillary lymph nodes. In addition, physical manifestations of any previously noted condition or adverse experience will be evaluated.

11.1.5. Laboratory Assessments

All abnormal laboratory values will be scored utilizing the ACTG toxicity grading system (see [Appendix 2](#)) where applicable or other appropriate criteria. Hematology and clinical laboratory evaluations will be performed by the

UMMS clinical laboratory facility. The following safety tests will be performed as outlined in the Schedule of Assessments ([Table 4](#)).

- Hematology: CBC, including differential, platelets
- Clinical Chemistries: serum electrolytes, liver function tests, renal function tests, PT/PTT
- Urinalysis: routine and microscopic, pregnancy test on women
- CD4 + T cell count
- HIV viral load by Roche-Amplicor ultra-sensitive RNA PCR

11.1.5.1. Hematology

CBC, including differential, platelets. The schedule is as outlined in [Section 6.1.1](#) and [Table 4](#).

11.1.5.2. Blood Chemistry

Serum electrolytes, liver function tests, renal function tests, PT/PTT will be performed as outlined in [Section 6.1.1](#) and [Table 4](#).

11.1.5.3. Urinalysis

Urinalysis will be performed as outlined in [Section 6.1.1](#) and [Table 4](#).

11.1.5.4. Virus Serology

Serologies for HIV, Hepatitis B and Hepatitis C will be performed as outlined in [Section 6.1.1](#) and [Table 4](#).

11.1.5.5. Pregnancy Screen

Serum pregnancy test will be performed at the screening visit. Subsequently urine pregnancy tests will be performed prior to each immunization and at the end of the study. It will also be performed if there is concern for pregnancy in a volunteer during the study.

11.1.5.6. Assessment of Vaccine Reactogenicity

The safety evaluation will include an evaluation of both local and systemic reactions to the candidate immunotherapeutic vaccines. Assessment of local reactogenicity will include erythema, induration, swelling, itching, pain and tenderness, skin discoloration, skin breakdown, and presence of subcutaneous nodules at the site of injection. Assessment of systemic reactions will include assessment of fever, chills, nausea, vomiting, arthralgia, myalgia, malaise, urticaria, wheezing, dizziness, headache. Each volunteer will complete a self-administered questionnaire/diary daily for 7 days after each immunization to assess reactogenicity. In addition, follow up telephone contact or clinic visit will be conducted by research nurse 24 to 48 hours following each immunization to record reactogenicity/adverse events. The study personnel will also conduct a careful assessment of possible adverse experiences at each clinic visit (See [Table 4](#)). Both the volunteer diary and the elicited adverse experiences will be used to determine the occurrence of adverse events. Any discrepancies between these sources will be resolved by careful review of the data with the volunteer. All adverse events will be recorded in the CRFs as noted in [Section 11.4](#).

11.2. Adverse and Serious Adverse Events

11.2.1. Definition of Adverse Events

11.2.1.1. Adverse Event (AE)

An adverse event is defined as any unfavorable or unintended change in body structure (signs), body function (symptoms) or laboratory result associated temporally with the use of study treatment, whether or not considered related to the study treatment. As defined by 21 CFR 312.32 (a), an unexpected adverse drug experience is:

“An adverse event or suspected adverse reaction is considered "unexpected" if it is not listed in the investigator brochure or is not listed at the specificity or severity that has been observed; or, if an investigator brochure is not required or available, is not consistent with the risk information described in the general investigational plan or elsewhere in the current application, as amended. For example, under this definition, hepatic necrosis would be unexpected (by virtue of greater severity) if the investigator brochure referred only to elevated hepatic enzymes or hepatitis. Similarly, cerebral thromboembolism and cerebral vasculitis would be unexpected (by virtue of greater specificity) if the investigator brochure listed only cerebral vascular accidents. "Unexpected," as used in this definition, also refers to adverse events or suspected adverse reactions that are mentioned in the investigator brochure as occurring with a class of drugs or as anticipated from the pharmacological properties of the drug, but are not specifically mentioned as occurring with the particular drug under investigation.”

All AEs that occur after any volunteer has signed consent or within 84 days following the cessation of immunizations and while being followed on the study protocol, whether or not they are related to the study, must be recorded on forms provided by the Institute of Human Virology.

11.2.1.2. Serious Adverse Event (SAE)

A serious adverse event is an AE occurring during any study phase (i.e., baseline, treatment, washout, or follow-up), and at any dose of the investigational product, comparator or placebo, that fulfills one or more of the following:

- Results in death
- It is immediately life-threatening (i.e., the volunteer was, in the opinion of the Investigator, at immediate risk of death from the event as it occurred).
- It requires in-patient hospitalization or prolongation of existing hospitalization
- It results in persistent or significant disability or incapacity (i.e., the event causes a substantial disruption of a person's ability to conduct normal life functions).
- Results in a congenital abnormality or birth defect
- Is an important and significant medical event that, based upon appropriate medical judgment, may jeopardize the patient or volunteer and may require medical or surgical intervention to prevent one of the other outcomes defining serious.

All SAEs that occur after any volunteer has signed consent or within 84 days following the cessation of treatment, and while on study protocol, whether or not they are related to the study, must be recorded on forms provided by the Institute of Human Virology.

Any serious adverse event (including death) due to any cause must be reported immediately to the principal investigator and the sponsor.

11.2.1.3. Other Adverse Event (OAE)

OAEs will be identified by the Drug Safety Physician and if applicable also by the Clinical Study Team Physician during the evaluation of safety data for the Clinical Study Report. Significant adverse events of particular clinical importance, other than SAEs and those AEs leading to discontinuation of the volunteer from the study, will be classified as OAEs. For each OAE, a narrative may be written and included in the Clinical Study Report.

11.3. Relationship to Study Drug

An Investigator who is qualified in medicine must make the determination of relationship to the investigational product for each AE. The Investigator should decide whether, in his or her medical judgment, there is a reasonable possibility that the event may have been caused by the investigational product. The relationship of an adverse event to the study medication will be determined by the investigator based on the following criteria.

1. Definitely Related:

- a. It follows a reasonable temporal sequence from vaccine administration
- b. It follows a known pattern of response to the vaccine
- c. Adverse event is most likely explained by vaccination than by other mechanisms. (It cannot be reasonably explained by the known characteristics of the volunteer's clinical state, environmental or toxic factors, or other modes of therapy administered to the volunteer)
- d. It appears on re-challenge with the vaccine or there is a local reaction at the injection site.

2. Probably Related:

- a. It follows a reasonable temporal sequence from vaccine administration
- b. It follows a known pattern of response to the vaccine
- c. Adverse event is more likely explained by vaccination than by other mechanisms. (It cannot be reasonably explained by the known characteristics of the volunteer's clinical state, environmental or toxic factors, or other modes of therapy administered to the volunteer)

3. Possibly Related:

- a. It follows a reasonable temporal sequence from vaccine administration.
- b. It follows a known pattern of response to the vaccine
- c. Adverse event is explained equally well by causes other than vaccination. (It may have been produced by the volunteer's clinical state, environmental or toxic factors, or other modes of therapy administration to the volunteer)

4. Not Related:

- a. It is clearly and incontrovertibly due to causes other than vaccination (e.g. disease, environment, etc.)
- b. It does not follow a reasonable temporal sequence from vaccine administration.
- c. It does not meet any of the criteria for vaccine relationship as listed under remotely related, possibly related or probably related.

If the relationship between the AE/SAE and the investigational product is determined to be “possible” or “probable” the event will be considered to be related to the investigational product for the purposes of expedited regulatory reporting.

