6.2. Number of Volunteers

The study population will consist of 60 healthy volunteers without HIV-1 infection who are available for at least 48 weeks of follow-up. Individuals of all races and groups may participate as long as the inclusion/exclusion criteria are met. The inclusion/exclusion criteria have been chosen to minimize risk to all participants. Therefore, those individuals with conditions that might place them at increased risk have been excluded.

Pregnant women and children are excluded from the trial as the safety of this vaccine has not previously been evaluated in humans and the effects on children or the unborn child are not known.

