6.4.1. Safety Criteria for Adjustment or Stopping Doses

1. If more than 5 volunteers in any group have an unexplained CD4 cell count decline (confirmed by assays at least 4 weeks apart) of greater than 30 percent and corroborated by a similar CD4% decline (>30%), immunizations in that study group will be stopped. No further immunizations will be allowed until after all data are reviewed by the IHV DSMB and the DSMB authorizes immunizations to continue in this group. Follow-up visits for safety will continue during this time. Note that an unexplained drop in CD4 cell count is defined as a decline that cannot be explained by an intercurrent illness or other event known to cause decreased CD4 cell counts.
2. The entire study will be stopped if five or more vaccine related severe (grade 3 or 4) adverse events occur in any group.
3. The volunteer will have immunizations stopped upon the occurrence of an unexpected Grade IV event felt by the investigator to be related to the study vaccine. No further immunizations will be allowed until after all data are reviewed by the IHV DSMB and the DSMB authorizes immunizations to continue in this group. Follow-up visits for safety will continue during this time.
4. The entire study immunizations will be stopped upon the occurrence of one unexpected serious adverse event felt to be related to the study vaccine.

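### Section 11.3 lists a known response pattern under every related category of a first-in-human vaccine, so a novel event with plausible timing may fit no category and rules that depend on relatedness may under-trigger

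*Combined protocol and SAP*

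**What the plan says.** Section 11.3 opens with a judgment test: the investigator decides whether "there is a reasonable possibility that the event may have been caused by the investigational product". It then says that the relationship "will be determined by the investigator based on the following criteria". Definitely, Probably and Possibly Related share the same first two items: a reasonable time sequence, and "It follows a known pattern of response to the vaccine". They differ in item (c), which grades how well vaccination explains the event against other causes, and in an extra item (d) for Definitely. No sentence says whether all lettered items must be met.

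Not Related has three items: another cause beyond dispute, no reasonable time sequence, and "It does not meet any of the criteria for vaccine relationship as listed under remotely related, possibly related or probably related". No remotely related category is defined, and definitely related is not named there. The section closes by saying that if the rating is possible or probable, "the event will be considered to be related to the investigational product for the purposes of expedited regulatory reporting". The sentence in 11.5.2 on SAEs discovered after the study names the same two ratings.

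Section 11.4 has causality recorded for each AE as 11.3 defines it. Section 6.2 states that "the safety of this vaccine has not previously been evaluated in humans". Under 11.2.1.1 an event is unexpected "if it is not listed in the investigator brochure or is not listed at the specificity or severity that has been observed". Section 6.4.1 item 4 stops all immunizations "upon the occurrence of one unexpected serious adverse event felt to be related to the study vaccine".

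**The concern.** A vaccine with no human safety record has little or no known pattern of response in humans. If a known pattern is a condition of relatedness, the events a first-in-human trial most needs to recognise are the hardest to class as related. Relatedness then decides whether most of the halting rules apply, whether a volunteer is withdrawn from further immunization under 7.3.1.1, whether DSMB members get the 48-hour notice in 11.6, and whether expedited reporting follows.

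The protocol's own main hazard shows the problem. Section 4.5.2 says the risk of auto-anti-CD4 antibodies drives the design, that depleting and non-depleting antibodies are both possible, and that the animal study saw no autoimmune response to CD4. A clinical event from such a response would have no observed pattern for this vaccine.

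**Working it through.** There is no stated figure to reproduce. The check sets the criteria against one another and then against each rule that uses them.

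**Step 1: joint or separate items?** Items (a) and (b) are identical in all three related categories. If any one item sufficed, plausible timing alone would make an event Definitely, Probably and Possibly Related at once. Of these two literal readings, only the joint one separates the categories.

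**Step 2: a novel event, plausible timing, no other evident cause.**

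| Category | Result under the joint reading |
|---|---|
| Definitely, Probably, Possibly Related | each fails on item (b) |
| Not Related (a) | not met: no other cause is established |
| Not Related (b) | not met: the timing is plausible |
| Not Related (c) | not met as worded: the timing item is one of the listed criteria and is satisfied |

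The event has no category. If (c) is instead read as failing every category as a whole, the event becomes Not Related. Neither result agrees with the reasonable-possibility sentence, under which the same event could be judged related.

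**Step 3: where relatedness is used.**

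| Needs unexpected and related | Needs related only | Needs neither |
|---|---|---|
| 6.4.1 items 3 and 4; 6.5 item 1; Grade 3/4 limb of 7.3.4 | 6.4.1 item 2; SAE limb of 7.3.4; withdrawal for toxicity in 7.3.1.1 | CD4-decline rule in 6.4.1 item 1 and 7.3.3 |

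The middle column does not need unexpectedness, but item (b) can still keep a novel event out of it.

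**Step 4: are unexpected and known pattern mutually exclusive?** No. Section 11.2.1.1 also counts as unexpected an event that is more severe or more specific than the brochure lists, and an event foreseen from the class or pharmacology but not mentioned for this product. Such an event can follow a pattern and still be unexpected. The first column of Step 3 is weakened, not emptied.

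**Step 5: illustration of scale.** Section 13.1 gives 45 vaccinees. Let r be the true rate of vaccine-caused unexpected SAEs per vaccinee and q the share of them classed as related. Both are assumptions; the documents give neither. With independent volunteers, the chance that 6.4.1 item 4 is met at least once is 1 − (1 − rq)^45.

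| r | q = 1 | q = 0.5 | q = 0.25 |
|---|---|---|---|
| 2% | 0.60 | 0.36 | 0.20 |
| 5% | 0.90 | 0.68 | 0.43 |
| 10% | 0.99 | 0.90 | 0.68 |

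For example, with r = 5% and q = 0.5, 1 − (1 − 0.025)^45 = 0.68.

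**Step 6: the reporting sentences.** Read literally, the expedited-reporting sentence in 11.3 and the post-study SAE sentence in 11.5.2 leave out the strongest rating, definite.

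**The case against.** A reader might infer that no unexpected event can be classed as related, so that the halting rules cannot fire. The documents do not support that. Section 11.3 nowhere says that all items are mandatory, and it leads with medical judgment. Step 4 shows that an event can be both unexpected and patterned. The rules speak of events felt or thought to be related and do not cite 11.3. An investigator could let item (c) decide and treat (a) and (b) as background. Patterns might also be argued from protein-vaccine experience (4.2) or the rabbit platelet finding (4.4.2).

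A reader might also infer that the primary safety result is biased downward. It is not: 13.4 defines the primary endpoints as severe systemic and severe local reactions, without reference to relatedness, and AEs are recorded whatever their cause (11.5.1).

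There are safeguards as well. The CD4 rule does not use relatedness. SAEs of any cause go immediately to the principal investigator and the sponsor. The DSMB reviews all AEs about every three months and can unblind or halt the study. It is also unlikely that staff would handle a Definitely Related event as unrelated.

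All of this limits the consequence, and it rules out the two stronger readings. It does not remove the contradiction. Letting item (c) decide is a sensible practice that the text does not state, while 11.4 sends the investigator to these criteria for every AE. The DSMB's 48-hour notice is itself tied to relatedness.

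**Conclusion.** The point holds as an internal contradiction in 11.3 with safety consequences. If the items apply jointly, a novel event with plausible timing has no related category, against the section's own reasonable-possibility standard. Rules that need relatedness may under-trigger, most of all the four that also need unexpectedness. The amount is unknown, because it depends on how investigators apply the list and on a brochure that is not among these documents; the probabilities in Step 5 only show how sensitive a one-event rule is to classification. Counts of related events could be too low. The omission of definite from two reporting sentences, and the faults in Not Related (c), stand on any reading. The correction should be made.

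**What to change.** In 11.3, state how the lettered items combine, and make the known-pattern item supportive rather than required, at least for Possibly Related, so that the criteria agree with the reasonable-possibility standard. If the change is confined to Possibly Related, its item (c) should also cover an event that vaccination explains at least as well as other causes. Otherwise a novel event with no rival explanation would still fail Probably on (b) and Possibly on (c).

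Add definite to the expedited-reporting sentence in 11.3 and the post-study SAE sentence in 11.5.2. In Not Related (c), replace remotely related with definitely related. Reconcile the wording with 11.2.1.1, 6.4.1, 6.5 and 7.3.4 without changing any halting threshold.

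The cost is a short wording amendment and a few more events classed as possibly related.

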11.4. Recording Adverse Events

Adverse events spontaneously reported by the volunteer and/or in response to an open question from the study personnel or revealed by observation will be recorded during the study at the investigational site. However, abnormal values that constitute an SAE or lead to discontinuation of administration of study drug must be reported and recorded

as an AE. Information about AEs will be collected from signing of consent until the end of the study. Serious Adverse Event information will be collected from signing of consent until 24 weeks following the last dose of study drug. The AE term should be reported in standard medical terminology when possible. For each AE, the investigator will evaluate and report the onset (date and time), resolution (date and time), intensity, causality (as defined in [Section 11.3](#)), action taken, serious outcome (if applicable), and whether or not it caused the patient to discontinue the study.

All adverse events occurring during the trial must be evaluated by the investigator and graded according to the adverse experience grading table ([Appendix 2](#)).

It is important to distinguish between serious and severe AEs. Severity is a measure of intensity whereas seriousness is defined by the criteria under [Section 11.2.1.2](#). An AE of severe intensity may not be considered serious.

Should a pregnancy occur, it must be reported and recorded on the Institute of Human Virology's pregnancy form. Pregnancy in itself is not regarded as an AE unless there is a suspicion that an investigational product may have interfered with the effectiveness of a contraceptive medication. However, it is a criterion for stopping immunizations in a volunteer as noted in [Section 6.1.1.6](#) and [Section 7.3.1.1](#).

The outcome of all pregnancies (spontaneous miscarriage, elective termination, normal birth or congenital abnormality) must be followed up and documented even if the patient was discontinued from the study.

All reports of congenital abnormalities/birth defects are SAEs. Spontaneous miscarriages should also be reported and handled as SAEs. Elective abortions without complications should not be handled as AEs.

